5.6 Outcome measures

5.6.1 Primary outcome measures

The primary outcome for this trial will be the efficacy of the Granulox spray in terms of wound healing.

Foot ulcer size, measured with Convated grid tool (week -2, 0, 3, 6, 9, 12)

5.6.2 Secondary outcome measures

This study also aims to record wound characteristics and patient-related outcomes measures, as well as safety endpoints.

- Size and characteristics of foot ulcer, determined with PUSH score (week -2, 0, 3, 6, 9, 12)
- Grading of foot ulcer, using Texas Univ grading score (week -2, 0, 3, 6, 9, 12).
- Wound closure status (week 0, 3, 6, 9, 12)
- Mobility score, as determined by LifeSpace questionnaire (week 0, 6, 12)

- Visual Analogue Pain score (week -2, 0, 3, 6, 9, 12)
- Quality of life score, determined with EQ5D-5L and Charing Cross Venous Ulcer Questionnaire (week 0, 6, 12)
- Wound status check [healed, not healed, recurrence] and any incidences of adverse events (week 18)
- Patient withdrawal rates due to change in management (e.g. need for surgery)
- Wound infection rates, any other adverse events
- Patient experience and satisfaction with the Granulox product and treatment regime

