HAWS; Haemoglobin Application to Wounds Study, a single-centre, controlled, prospective randomized trial

Version 6, dd 10July 2018

Chief Investigator's Statement of Ownership and Content.

I, [name], confirm that this protocol is my work and is owned by me. The protocol conforms with standards outlined in the Declaration of Helsinki 1964.

Name (PRINT): [name]

Signature:

Date: LATH SEP. 2018

RESEARCH PROTOCOL SUMMARY

TITLE:	Haemoglobin Application to Wounds Study, a single-centre, controlled, prospective, randomized trial of Granulox
	haemoglobin spray for adjuvant treatment of foot ulcers
Short title:	HAWS; Haemoglobin Application to Wounds Study
IRAS number	227421
Device description	Granulox® Medical device. Class III, CE 0482
	Indications: Granulox® is a spray for use on chronic wounds. Granulox® is an innovative medical device for the proposed treatment of chronic wounds, such as venous leg ulcer, arterial leg ulcer, mixed leg ulcer, foot ulcers, secondary healing of surgical wounds and pressure sores. Granulox® can also be used on sloughy and infected wounds. Each canister contains 12 ml of spray, sufficient for 30 wound treatments.
Study design	Single-centre, controlled, prospective randomized trial
Primary objective	To determine the efficacy of the Granulox spray as an adjuvant therapy for foot ulcers at 3, 6, 9 and 12 weeks post-baseline - Healing rate (ulcer size; 12 weeks is endpoint for power calculation), as measured with surface area scoring grid
Secondary objectives	Clinical assessment at -2, 0, 3, 6, 9 and 12 weeks, and - PUSH ulcer size/grading score - Texas Univ grading score - Wound closure Safety of Granulox spray throughout trial duration, up to 12 weeks - Wound infection incidence; secondary interventions Patient-reported outcome measures at 0, 6 and 12 weeks - Patient mobility score (LifeSpace questionnaire) - Quality of life score (EQ-5D-5L and CWIQ) - Visual Analogue Score for pain associated with DFU Status of wound at week 18 - Healed, not healed, recurrence.
Patient population	A total of 60 participants, over the age of eighteen, with measurable foot ulcer, treated in clinic. Forty patients to have a DFU and further 20 patients to have nondiabetes related foot

	Indiana B. III in the second s
	ulcer. Participants must have the capacity to provide informed written consent and complete patient reported outcome measures.

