5.3 Consent

Those eligible will be approached and provided with an information pack and consent form, which will be signed to indicate that informed consent has been given. Patients will be given ample time to consider taking part, more than 24 hours if they wish. The direct healthcare professional will first approach a patient about the study, and after verbal consent by the patient the healthcare professional themselves or a member of the research team can go through the informed consent process.

Patients are also allowed to consent to taking part when first approached as long as the study has been discussed with the patient and they have been given time to read the patient information leaflet and opportunity to ask any questions that they may have. Participants will receive no incentives and consent will be regarded as a process and not a one-off event. Participants are free to withdraw from the study at any time without the need to give any reasons for withdrawal. Their standard of care will not be affected by either declining to participate in the study or withdrawing during participation. Data collected up to the date of withdrawal will be retained for analysis.

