6. SUBJECTS

6.1 Anticipated number of research subjects

There is pilot data to base a *priori* sample size calculation on, but this concerns a single retrospective study (Hunt and Elg, 2016). In their study, they observed 37% (control) and 89% (Granulox) wound size change versus baseline measurement at 12 weeks. This would mean that 14 patients (7 in each arm) would be sufficient to have the trial powered to 80%. For this present trial, a more conservative approach is taken, see Table 4. The earlier published average healing rate of 25% is used as the anticipated minimum healing rate (Margolis, 1999). Since some patients may require surgical intervention or may withdraw, a hypothetical 20% dropout rate is calculated into the sample size (actual attrition rate is a study objective). A theoretical 1:1 allocation to the control and Granulox intervention group respectively will be applied. However, because the PUSH score is not known beforehand this may not be achieved if more patients are recruited into one of the two PUSH cohorts. Diabetic foot ulcers (DFUs) and other foot ulcers will be randomised from separate randomisation lists.

The primary outcome, average percentage decrease in ulcer size between baseline and 12 week follow-up is used for sample size calculation. Power calculations for sample size, 80% power and 5% significance, based on two-sided Mann-Whitney U-test. A priori power calculations using GPower 3.1 software, result in the following sample size summarized in Table 4. This is based on the DFU study by Hunt and Elg. A further 20 patients with non-diabetic foot ulcers will be recruited to pilot what impact Granulox has on those types of wounds.

Table 4, Sample size calculation

	Median change in DFU ulcer size at 12 weeks (presume decrease for both arms, ie one-tailed approach)	Standard Deviation
Arm A (hypothetical)	52%	30%
Arm B (hypothetical)	25%	30%
	Power beta of 80%, Alpha p-value of Sample size required without any dro	

Sample size with 20% attrition rate included: 40

Total of 40 DFU patients:

- 20 Patients to receive treatment as usual (TaU)
- 20 Patient to receive TaU plus Granulox spray

Plus 20 non-DFU foot ulcers:

- 10 Patients to receive treatment as usual (TaU)
- 10 Patient to receive TaU plus Granulox spray

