The CONSORT guidelines require a statement on the number of patients assessed for eligibility (Schulz, Altman & Moher 2010). The number of patients screened but who did not meet the inclusion criteria or who declined to participate will be recorded, as will any patients who are lost to follow-up (Appendix 3).

The calculation does take into account a 10% patient attrition rate (withdrawal and loss to follow-up), since this involves a study with at least two visits. Patients will be recruited from the adult (age 18+) population routinely seen by the evaluating clinical staff members.

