6.3 Early withdrawal of subjects

Patients have the right to withdraw from the trial at any time and without giving any reason. If a patient withdraws from the trial, any and all information gathered prior to the withdrawal will be excluded in the analysis, no further data collection will occur. If a patient does not attend a planned follow-up appointment then two more attempts will be made to contact the patient regarding the study. If still no contact can be made then the patient is deemed lost to follow-up and any collected study data will be retained.

If a female patient finds out that she is pregnant during the course of participating in the study, they will be requested to inform the research team immediately. The participant will be withdrawn from the study if allocated to the Granulox arm. Since the study is not blinded, there is no requirement for an unblinding procedure.

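### The protocol does not separate a change in management such as surgery from withdrawal, so its stop-collection rule may remove week-12 primary data in patients who still consent

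*Protocol*

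**What the plan says.** Four places in the protocol bear on what happens to a patient whose management changes.

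- Section 5.6.2 lists as a secondary outcome "Patient withdrawal rates due to change in management (e.g. need for surgery". The word used for these patients is withdrawal.
- Section 6.1 justifies the attrition allowance thus: "Since some patients may require surgical intervention or may withdraw, a hypothetical 20% dropout rate is calculated into the sample size". Surgery is counted within dropout.
- Section 6.3, the only section on withdrawal, opens with the patient's right to leave and then states "any and all information gathered prior to the withdrawal will be excluded in the analysis, no further data collection will occur".
- Section 5.3 says the opposite about earlier data: "Data collected up to the date of withdrawal will be retained for analysis".

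The endpoint at risk is defined in 6.1: "The primary outcome, average percentage decrease in ulcer size between baseline and 12 week follow-up is used for sample size calculation". Section 8.2 compares the arms on it by Mann-Whitney test with week 12 as primary. Section 5.5 keeps patients in the study for 18 weeks and has the researcher telephone at week 18. The protocol summary also names "Wound infection incidence; secondary interventions" among the safety measures.

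**The concern.** Leaving the study and changing treatment are different events. A patient who withdraws consent for data collection cannot be measured. A patient who goes for surgery and still consents can be, and in a randomised comparison should be. The protocol uses one vocabulary for both and gives one rule, which stops collection.

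If site staff apply that rule to surgical cases, the week-12 value is missing for a group defined by something that happened after randomisation. Need for surgery plausibly goes with poor healing. Section 6.1.1 says neither participants nor researchers are blinded, so knowing the allocation could also influence the decision to change management. If such changes are more frequent in one arm, the week-12 comparison is made between differently selected groups. An analysis plan can say how to handle missing values, but it cannot recover measurements that were never taken.

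**Working it through.** **1. Reading the passages together.** Section 5.6.2 calls a management change a withdrawal and 6.1 counts surgery as dropout. Section 6.3 offers two routes: withdrawal (collection stops) and loss to follow-up (only after failed contact attempts). A consenting surgical patient is not out of contact, so the only rule that could cover the case is the first. No section schedules measurements after a change in management.

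**2. The plan's own figure.** Table 4 inputs: 52% v 25% (difference 27), SD 30%, alpha 5%, power 80%, one-tailed.

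- n per arm = 2 × (1.645 + 0.842)² × (30/27)² = 15.3, so 16
- total 32; 32 / (1 − 0.20) = 40

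This matches the stated 40 diabetic foot ulcer patients, 20 per arm. It reproduces only one-tailed; the text of 6.1 names a two-sided test, which is a separate matter. The planned loss is 0.20 × 40 = 8 patients without a week-12 value.

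**3. Illustration of bias.** Assumptions that the protocol does not give: the 8 losses split as 6 of 20 controls (30%) and 2 of 20 Granulox patients (10%); change is normally distributed; Arm A of Table 4 is Granulox; dropout propensity correlates ρ with poor healing. If a fraction p is lost, the mean among those remaining is

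μ + ρ × 30 × φ(z_p) / (1 − p)

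- p = 0.30: φ(−0.524)/0.70 = 0.348/0.70 = 0.497, a shift of 14.9ρ
- p = 0.10: φ(−1.282)/0.90 = 0.1755/0.90 = 0.195, a shift of 5.85ρ

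| | ρ = 1 (only the worst healers leave) | ρ = 0.5 |
|---|---|---|
| Control mean | 25 + 14.9 = 39.9 | 25 + 7.45 = 32.45 |
| Granulox mean | 52 + 5.85 = 57.85 | 52 + 2.9 = 54.9 |
| Observed difference (true 27) | about 18 | about 22.5 |
| Observed difference (true 0) | 30.85 − 39.9 = about −9 | 27.9 − 32.45 = about −4.5 |

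Reversing the split reverses the sign: with no true effect, about 9 or 4.5 points in favour of Granulox.

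**4. Simulation** (20 per arm, two-sided Mann-Whitney at 5%, 10,000 runs):

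| Loss, control/Granulox | ρ | Mean difference, true 27 | Power | Rejection, true 0 |
|---|---|---|---|---|
| none | – | 27.1 | 78% | 5% |
| 30%/10% | 0 (random) | 27.1 | 65% | 4% |
| 30%/10% | 0.5 | 22.6 | 53% | 7% |
| 30%/10% | 1 | 18.1 | 50% | 19% |
| 10%/30% | 0.5 | 31.3 | 80% | 7% |
| 10%/30% | 1 | 35.6 | 95% | 19% |
| 20%/20% | 0.5 | 26.9 | 69% | 6% |
| 20%/20% | 1 | 27.1 | 83% | 9% |

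The row with random loss separates the two effects. Of the fall from 78% to 50% in the worst case, 13 points (78 to 65) come from having 8 fewer patients, which the plan budgets for, and 15 points (65 to 50) from selective loss. With equal loss the difference is not biased.

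**The case against.** The strongest objection is that the protocol nowhere says surgery ends data collection. The stop rule in 6.3 follows a sentence on the patient's right to leave. The one trial-initiated withdrawal that 6.3 names is pregnancy in the Granulox arm; surgery is not mentioned. Section 6.1 joins surgery and withdrawal with 'or', as if they were different things, and 5.5 keeps patients in for 18 weeks. This stands: a reader might infer an outright rule that surgical patients are no longer measured, and the text does not support so strong a statement. What remains is that 5.6.2 uses the word withdrawal for these patients and no section tells staff to continue.

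Three further inferences are tempting and not supported.

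- *That the patients lost are those in whom treatment failed.* Surgery is given only as an example of a management change, and neither its type nor its link to ulcer response is stated. A relation to healing is plausible, not documented.
- *That safety events would be missed.* The event itself is captured: management change, infection, adverse events and secondary interventions are all listed. Only follow-up after the event is in doubt.
- *That a bias of 9 points is to be expected.* It needs the whole 20% allowance, which also covers ordinary withdrawals, to fall on the worst healers and to split three to one. With no true effect, and surgery driven only by healing, the arms would lose patients equally. A false difference then needs another source of imbalance, such as open-label decisions.

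How surgical cases are scored in the analysis may properly sit in an analysis plan that is not shown here. Whether they are measured cannot be left there.

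**Conclusion.** The point holds as an ambiguity with consequences for the primary endpoint. Sections 5.6.2, 6.1 and 6.3 read together would end measurement, including week 12 and the week-18 call, for consenting patients whose management changes. The protocol neither states this outright nor provides otherwise.

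The direction and size of any bias depend on the split by arm and on how strongly dropout tracks healing; the protocol gives neither. For a 30%/10% loss, the 27-point difference would appear as about 18 points in the worst case and about 23 at a correlation of 0.5. With no true effect, the false difference would be about 9 or 4 to 5 points, with rejection just under 20% or about 7% against a nominal 5%. These show what is possible and are not forecasts. If the arms lose patients equally, the difference is not biased.

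Two conflicts aggravate the matter. If 6.3 prevails over 5.3 on earlier data, the week 3, 6 and 9 values are lost too. And 6.1 gives a second attrition figure ("The calculation does take into account a 10% patient attrition rate (withdrawal and loss to follow-up") beside the 20%, so the expected loss is itself unsettled.

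**What to change.** - In 6.3, define two states. (a) Withdrawal of consent for data collection: collection stops. (b) Stopping Granulox or a change in management, with consent continuing: the patient stays in the study, scheduled ulcer measurements continue to week 12, the week-18 call is made, and the date and type of intervention are recorded. This concerns data collection only and alters no clinical decision.
- In 5.6.2, rename the outcome *rate of change in management*, and report withdrawal of consent separately.
- Reconcile 5.3, 5.6.2, 6.1 and 6.3: whether data before withdrawal are kept, whether surgery counts as dropout, and which attrition figure applies.
- Prespecify how surgical cases enter the Mann-Whitney comparison, since an ulcer removed by surgery should not pass unexamined as healed. Worst rank is one option. It is a debatable choice and may sit in the statistical analysis plan.

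The cost is a protocol amendment of a few sentences. Clinic staff already measure the ulcer at scheduled visits and week 18 is already a telephone call. The small downside is that some visits must be arranged around hospital care, and some surgical patients may be harder to reach through podiatry clinics.

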6. SUBJECTS

6.1 Anticipated number of research subjects

There is pilot data to base a *priori* sample size calculation on, but this concerns a single retrospective study (Hunt and Elg, 2016). In their study, they observed 37% (control) and 89% (Granulox) wound size change versus baseline measurement at 12 weeks. This would mean that 14 patients (7 in each arm) would be sufficient to have the trial powered to 80%. For this present trial, a more conservative approach is taken, see Table 4. The earlier published average healing rate of 25% is used as the anticipated minimum healing rate (Margolis, 1999). Since some patients may require surgical intervention or may withdraw, a hypothetical 20% dropout rate is calculated into the sample size (actual attrition rate is a study objective). A theoretical 1:1 allocation to the control and Granulox intervention group respectively will be applied. However, because the PUSH score is not known beforehand this may not be achieved if more patients are recruited into one of the two PUSH cohorts. Diabetic foot ulcers (DFUs) and other foot ulcers will be randomised from separate randomisation lists.

The primary outcome, average percentage decrease in ulcer size between baseline and 12 week follow-up is used for sample size calculation. Power calculations for sample size, 80% power and 5% significance, based on two-sided Mann-Whitney U-test. A priori power calculations using GPower 3.1 software, result in the following sample size summarized in Table 4. This is based on the DFU study by Hunt and Elg. A further 20 patients with non-diabetic foot ulcers will be recruited to pilot what impact Granulox has on those types of wounds.

Table 4, Sample size calculation

	Median change in DFU ulcer size at 12 weeks (presume decrease for both arms, ie one-tailed approach)	Standard Deviation
Arm A (hypothetical)	52%	30%
Arm B (hypothetical)	25%	30%
	Power beta of 80%, Alpha p-value of Sample size required without any dro	

Sample size with 20% attrition rate included: 40

Total of 40 DFU patients:

- 20 Patients to receive treatment as usual (TaU)
- 20 Patient to receive TaU plus Granulox spray

Plus 20 non-DFU foot ulcers:

- 10 Patients to receive treatment as usual (TaU)
- 10 Patient to receive TaU plus Granulox spray

The CONSORT guidelines require a statement on the number of patients assessed for eligibility (Schulz, Altman & Moher 2010). The number of patients screened but who did not meet the inclusion criteria or who declined to participate will be recorded, as will any patients who are lost to follow-up (Appendix 3).

The calculation does take into account a 10% patient attrition rate (withdrawal and loss to follow-up), since this involves a study with at least two visits. Patients will be recruited from the adult (age 18+) population routinely seen by the evaluating clinical staff members.

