To further illustrate the point concerning the impact of foot ulcers: the healing rate of DFUs is poor; on average, 24% of wounds have healed by week 12 of treatment, and only 31% at 20 weeks of treatment (Margolis, 1999). A cohort study involving 31 diabetic patients determined that the average healing time for neuropathic DFUs is 78 days whereas this increases to 133 days for patients with additional peripheral vascular disease (Zimny et al, 2002). Further analysis has shown that the size of the ulcer negatively correlates to the healing rate, whereas a patient's age, sex, or type of diabetes is not associated with a change in healing rate outcome (Oyibo, 2001). DFU healing progress at 4 weeks of treatment is a predictor of the likelihood that the wound will be healed by 12 weeks of treatment. If the wound has not healed by at least 50% after 4 weeks, the likelihood that the DFU will be completely healed by 12 weeks is reduced to circa 10% (Sheehan, 2003). Taken together, there is a major group of patients with DFU -those with larger ulcers, and co-morbidities, responding poorly to standard treatment in the first 4 weeks – that is at risk of ending up with long-term wounds taking over 3 months to heal, if at all.

Oxygen is an essential component of the wound healing process (Hunt et al, 1969). Poor circulation due to diabetic angiopathy impairs the healing process and limits the degree of required growth factor release and angiogenesis (Falanga, 2005; Mathieu et al, 2006). Increasing oxygen levels can be achieved in various ways, including hyperbaric chamber treatment (Faglia, 1996). However, this method is costly, cumbersome and logistically challenging. A novel haemoglobin spray that is designed to enhance wound healing, including non-diabetic foot ulcers and DFUs, by enriching the wound area with oxygen using porcine haemoglobin is now available in the UK. The product is called Granulox and it marketed by InFirst Healthcare Ltd. The mode of action is the application of porcine haemoglobin onto a wound to facilitate increase oxygen levels through diffusion into the wound area (Arenberger et al, 2011; Norris, 2014; Hunt & Elg, 2016). Hunt & Elg, in a study with retrospective analysis of standard care DFUs and prospective assessment of Granulox adjunct therapy DFUs, have shown that the healing rate for chronic wounds is much accelerated with haemoglobin treatment. Figure 1 summarises their data.

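### Table 4's control value of 25% comes from a proportion of wounds healed but is used as a percentage reduction in ulcer size, so the planned 27-point difference is not derived on the primary-outcome scale.

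*Protocol*

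**What the plan says.** Section 6.1 names the outcome used for sizing: "The primary outcome, average percentage decrease in ulcer size between baseline and 12 week follow-up is used for sample size calculation". The column in Table 4 is headed "Median change in DFU ulcer size at 12 weeks", and its two rows give 52% for Arm A and 25% for Arm B, each with an SD of 30%.

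The 25% is tied to the cited 1999 meta-analysis of standard treatment: "The earlier published average healing rate of 25% is used as the anticipated minimum healing rate". The Introduction describes what that source reported: "on average, 24% of wounds have healed by week 12 of treatment, and only 31% at 20 weeks of treatment".

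Section 6.1 also quotes a pair of figures that are on the size-change scale, from the pilot study: "they observed 37% (control) and 89% (Granulox) wound size change versus baseline measurement at 12 weeks". No source is given for Arm A's 52%; both rows of Table 4 are labelled hypothetical.

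**The concern.** A proportion of wounds healed and a median percentage reduction in area are different quantities. The first counts patients who reach closure. The second is the centre of a continuous distribution across all patients, healed or not. Neither can be read off the other without knowing how the unhealed wounds behave. The protocol itself keeps them apart: ulcer size is the primary outcome in section 5.6.1 and wound closure is a secondary outcome in section 5.6.2.

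The phrase healing rate covers both meanings, which is probably how the figure crossed over. As a result, one of the two values that define the planned difference belongs to another outcome, and the other has no source. This calculation is the only justification for 40 DFU patients. If the trial finds no difference, readers will judge that result against an effect it was said to be powered for, although that effect was never established on the scale analysed.

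**Working it through.** **Inputs.** From section 6.1 and Table 4: Arm A 52%, Arm B 25%, SD 30% in both arms, alpha 5%, power 80%, 1:1 allocation, 20% attrition, 40 DFU patients. The text names a two-sided Mann-Whitney U-test; Table 4 says one-tailed. Reading Arm B as control is an inference, but a firm one: its figure comes from a standard-treatment source and is called the minimum rate. The 24% in the Introduction and the 25% in section 6.1 appear to be the same figure, rounded.

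**Step 1. Reproduce the stated 40.** The difference is 52 − 25 = 27 points, so d = 27/30 = 0.90. With the one-sided normal formula, n per arm = 2 × (1.645 + 0.842)² / 0.90² = 15.3, rounded up to 16. The total is 32, and 32/0.8 = 40. A noncentral t calculation also gives 16 per arm. The stated figure therefore reproduces one-sided. The two-sided Mann-Whitney test named in the text needs 22 per arm, or 44 before attrition and 44/0.8 = 55 with it.

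**Step 2. Compare the scales.**

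| Figure | Scale in the protocol | Where |
|---|---|---|
| 24% | proportion of wounds healed by week 12 | Introduction |
| 25% | the same source, entered as median change in ulcer size | section 6.1, Table 4 |
| 37% control, 89% Granulox | change in wound size at 12 weeks | section 6.1 |
| 52% | median change in ulcer size, no source | Table 4 |

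The arithmetic in step 1 is sound. What fails is the origin of an input.

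**Step 3. How much could it matter?** Mann-Whitney power is taken from a noncentral t distribution with the per-arm size multiplied by 3/π (efficiency under normal data). For 16 per arm the effective size is 16 × 0.955 = 15.28, the degrees of freedom are 2 × 15.28 − 2 = 28.6, and the noncentrality is d × √(15.28/2) = 2.764 × d.

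| Scenario (SD 30%, 16 evaluable per arm) | Difference | d | Two-sided power | One-sided power |
|---|---|---|---|---|
| 52% vs 25%, as in Table 4 | 27 | 0.90 | 67% | 78% |
| 52% vs 37%, sensitivity case | 15 | 0.50 | 27% | 38% |
| 64% vs 37%, 27 points kept | 27 | 0.90 | 67% | 78% |

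In the sensitivity case, 80% power would need 67 per arm (two-sided Mann-Whitney).

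**Step 4. Detectable difference.** Solving the same formula for 80% power at 16 per arm and SD 30%, two-sided, gives 31.5 points. This depends on the SD, the sample size and the test, and not on the control level. The gap between 31.5 and 27 points, and the 67% power at 27 points, therefore come from the two-sided Mann-Whitney test and not from the 25%.

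**The case against.** The strongest reply is that power depends on the difference and the SD, so the control level alone changes nothing. That is correct. A reader might infer that correcting the control value nearly halves the planned difference, from 27 to 15 points. That follows only if the unsourced 52% is kept while the control value alone moves to 37%. The same pilot sentence gives 89% for Granulox, so the protocol's one pair of size-change figures is 89 − 37 = 52 points apart, about twice the planned difference. The documents do not show that 27 points is too large.

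A reader might also conclude that calling the plan conservative is false, because a lower control value widens the gap. Section 6.1 makes that claim for the whole approach against the pilot-based 14 patients. On that comparison it is true: 27 points against 52, and 40 patients against 14.

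Nor do the documents establish 37% as the right planning value. It comes from the single retrospective study that section 6.1 declines to rely on alone. Section 6.1.1 admits to randomisation only wounds that healed by less than 50% in the two-week run-in, which removes fast healers and makes a lower control value plausible. It is also not safe to argue that 24% closure implies a median reduction above 25%: unhealed wounds can enlarge, and the protocol does not describe their course. Finally, 52 equals the pilot's between-arm difference, but nothing in the text shows that this is more than coincidence.

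These points limit the size of the problem. They do not remove it: a proportion healed still stands in Table 4 as a change in ulcer size.

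**Conclusion.** The control input in Table 4 is wrong as written. By the protocol's own account it is a proportion of wounds healed, and it is used as a median reduction in ulcer size. With the 52% unsourced as well, neither end of the 27-point difference is supported on the primary-outcome scale.

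The consequence for power is conditional. Two-sided power at 16 evaluable per arm is about 27% (about 38% one-sided) if the true pair were 52% and 37%; it is unchanged if a 27-point difference is justified on other grounds. These figures assume SD 30%, normally distributed data and 20% attrition. The scale mismatch itself needs none of these assumptions. The conflict between the two-sided text and the one-tailed table is a separate defect. It accounts for the stated 40 reproducing only one-sided and is not evidence about the 25%.

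**What to change.** In section 6.1 and Table 4:

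- Remove the healed-proportion figure as a size-change input.
- State a sourced size-change assumption for each arm. The pilot's 37% is the one control figure available; if a lower value is preferred, for example because of the run-in, say why. Give the basis for Arm A.
- Restate the calculation as a detectable difference: with 32 evaluable DFU patients, SD 30% and the two-sided Mann-Whitney test at 5%, power is 80% at about 31.5 points and about 67% at 27 points.

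This rewords one section and one table. It needs no extra patients, visits or measurements. The cost is a less favourable stated figure than the present 80% at 27 points.

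### Section 6.1 states a two-sided Mann-Whitney test with 80% power, but the 40 DFU patients come from a one-tailed calculation; two-sided power in that cohort is about 67% with the planned 20% attrition

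*Protocol*

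**What the plan says.** Protocol section 6.1 sizes the diabetic foot ulcer (DFU) cohort on the percentage decrease in ulcer size from baseline to week 12. On the test it says: "Power calculations for sample size, 80% power and 5% significance, based on two-sided Mann-Whitney U-test".

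Table 4, in the same section, heads its effect column with the words "presume decrease for both arms, ie one-tailed approach". It assumes a 52% decrease in one arm and 25% in the other, each with SD 30%, and concludes: "Sample size with 20% attrition rate included: 40", that is, 20 per arm.

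Two paragraphs on, still within 6.1, the attrition allowance changes: "The calculation does take into account a 10% patient attrition rate".

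Section 8.2 names the Mann-Whitney U-test for the primary comparison and gives no sidedness. Section 6.1 describes a further 20 patients with non-diabetic ulcers as a pilot.

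**The concern.** The sample size cannot be both two-sided and one-tailed, and both statements are legible in the same section. The reason offered for one tail is also not a reason. A one-tailed test concerns the sign of the difference between arms, and an expectation that ulcers shrink in both arms leaves that sign open.

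What is at stake is how the result will be read. If the two-sided test is the one applied, a null result would be presented as coming from a trial with 80% power. On the Protocol's own inputs and its planned attrition, the chance of missing the assumed effect in DFU patients is nearer one in three. The two attrition figures add to this, because a reader cannot tell how many evaluable patients the stated power assumes.

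**Working it through.** **Inputs, all from Protocol section 6.1.** Decreases of 52% and 25%, so a difference of 27 points; SD 30% in each arm; 5% significance; 80% power; 1:1 allocation; 40 DFU patients with 20% attrition included. Standardised difference: d = 27/30 = 0.90.

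The Table 4 cells for alpha and for the size before dropout are cut off in the text available. Alpha is therefore taken from the sentence above the table, and the pre-dropout size is back-calculated: 40 × 0.8 = 32 evaluable, 16 per arm.

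**Reproducing the stated 40.** The normal approximation is n per arm = 2(z_alpha + z_beta)²/d².

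- One-tailed: 2(1.645 + 0.842)²/0.81 = 15.3, so 16 per arm, 32 in total, and 32/0.8 = 40. This is an exact match.
- Two-sided: 2(1.960 + 0.842)²/0.81 = 19.4, so 20 per arm, 40 in total before dropout, and 40/0.8 = 50.

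The table below uses the noncentral t distribution. For the Mann-Whitney rows, n is multiplied by the asymptotic relative efficiency (ARE) 3/π, which assumes normal data.

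| Test | Per arm for 80% | Evaluable total | With 20% attrition (÷ 0.8) |
|---|---|---|---|
| t, one-tailed | 16 (power 80.0%) | 32 | 40 |
| Mann-Whitney, one-tailed | 17 (80.6%) | 34 | 43 |
| t, two-sided | 21 (81.2%) | 42 | 53 |
| Mann-Whitney, two-sided | 22 (81.2%) | 44 | 55 |

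So 40 with attrition included comes from a one-tailed t or normal calculation. A one-tailed Mann-Whitney calculation comes close but does not give it (43, or 34 × 1.2 = 40.8, so 41, if attrition is added by multiplication).

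**Power of the stated two-sided 5% Mann-Whitney test in the DFU cohort.** Effective size m = n × 3/π per arm; noncentrality d√(m/2); degrees of freedom 2m − 2. For n = 16: m = 15.28, noncentrality 0.90 × √7.64 = 2.488, df = 28.56, critical t = 2.047, power 67.1%.

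| Evaluable per arm | Attrition from 40 | Power (ARE method) | Power (simulation, normal data, 20,000 runs) |
|---|---|---|---|
| 16 | 20% | 67.1% | 65.5% |
| 18 | 10% | 72.6% | 72.0% |
| 20 | none | 77.2% | 77.1% |
| 22 | not reachable with 40 | 81.2% | 80.3% |

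**Difference detectable with 80% power at 16 per arm.** A difference of 31.5 points (d = 1.05) gives 80.0%. A difference of 31 points gives 78.8%.

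**All 60 patients pooled.** 60 × 0.8 = 48 evaluable, 24 per arm. With the same d = 0.90, two-sided Mann-Whitney power is 84.6%.

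**The case against.** The contradiction between the text and Table 4 cannot be argued away, but its size can be contested on four grounds.

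- **The 67% is conditional.** It is the lowest of three figures and needs the full 20% attrition. With nobody lost, power is 77%. This stands, and the figure should carry its condition. The 20% is nevertheless the allowance on which Table 4 rests its own 80%.
- **The data may not be normal.** The Protocol states no parent distribution. By the same ARE method, a logistic parent gives 73.5% at 16 per arm and 82.9% at 20; a Laplace parent gives 86.3% at 16; the minimum-ARE option gives 62.4%. A reader might infer from the tables above that 40 patients can never give 80% two-sided power. The documents do not support that. However, none of these options turns a two-sided calculation with 20% attrition into 40: they give 48, 35 and 60 respectively.
- **The analysis may include all 60.** The objectives and section 8.2 speak of foot ulcers without restriction, and pooling gives about 85%. Against this, section 2 names DFU healing as the primary outcome, and 6.1 bases its calculation on DFU patients and calls the other 20 a pilot. The pooled figure also needs the same effect and SD in non-diabetic ulcers. It remains a conditional alternative.
- **The mismatch is not purely one of tails.** A one-tailed Mann-Whitney calculation needs 17 per arm, so part of the gap may come from using a t or normal formula. This stands.

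A reader might also be tempted to use the figure of 7 per arm, derived in 6.1 from the earlier retrospective study, as evidence of which sidedness was used. It cannot serve, because the Protocol gives no SD for that study. Nor do the documents show any intention to report a one-sided p-value; the only sentence that attaches a sidedness to the named test says two-sided.

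**Conclusion.** The point holds for the DFU cohort that the calculation was made for. Section 6.1 contradicts itself on sidedness, justifies one tail by an argument that does not bear on it, and gives two attrition figures. The stated combination of two-sided test, 5% level, 80% power and 40 patients with 20% attrition does not follow from the stated inputs.

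The shortfall is about 13 points of power at the planned attrition (67% against 80%), 7 at 10% attrition and 3 with no dropout. These figures rest on roughly normal data, equal arms and the Table 4 effect and SD. They are not an unconditional statement that the trial has 67% power: that depends on who is lost, on the distribution, and on whether the primary population is the 40 DFU patients or all 60.

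**What to change.** In section 6.1:

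- Delete the one-tailed phrase from Table 4 and keep the two-sided 5% test.
- Use one attrition figure, 20%, in both places.
- Restate the power along these lines: *40 DFU patients (32 evaluable) give about 67% power (two-sided 5% Mann-Whitney, normal data) for 52% against 25% with SD 30%, and 80% power for a difference of about 31.5 points.*

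In section 8.2, add that the Mann-Whitney test is two-sided at 5%.

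If the primary analysis population is all 60 randomised patients, say so and state about 85% power (48 evaluable), with the assumption of the same effect and SD in non-diabetic ulcers.

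The cost is a change of wording and a less favourable stated power for the DFU cohort; no patients are added. Keeping 80% for that cohort on these inputs would instead need 44 evaluable, or 55 with 20% attrition (56 for equal arms).
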